## 3.5.1.3 Sociodemographic and Clinical Characteristics

**Table** 4 4 summarizes the definition and timing of the sociodemographic and clinical outcomes that will be collected, if available, from routine clinical practice visits. Completeness of all variables (e.g., race) may be dependent on country-specific data privacy regulations.

Variables	Definition	Timing
Patient demographics and vital signs		
Sex	Male/Female	
Race (if allowed)	White, Black or African American, Asian, American Indian or Alaska Native, Native Hawaiian or Other Pacific Islander, Other, Not collected at site	
Ethnicity (if allowed)	Hispanic or Latino, Not Hispanic or Latino, Japanese, Not Japanese, Not collected at site	
Country	US, Germany	Baseline
Age	Calculated from year of birth to Day 0	Busenne
Height	Units	
Weight	Units	A 11: -: - : - 1
BMI	Derived from weight and height	All Visits 
Medical history		
History of other primary malignancies and details	Yes/No, details information including, primary site, date of diagnosis and stage	Baseline

Table 4. Sociodemographic and Clinical Characteristics Definitions and Timing

Variables	Definition	Timing
Smoking	Current, Past, Never	
Alcohol use	Yes/No, duration, volume per week	
Previous enrollment in an interventional study (RCTs) and details	Yes/No, date of enrollment; treatment, start and end date	
Comorbidities and details	Diagnosis date and name of diagnosis, grouped using the National Cancer Institute (NCI) Comorbidity Index.	Baseline and all visits 
Disease characteristics		
Initial diagnosis	Date of initial diagnosis	
Disease stage at initial diagnosis	EC/GEJC stage (i.e., I, II or III) and stage using TNM system	
Tumor location at initial diagnosis	EC (upper, middle, lower area of the esophagus) or GEJC (Siewert type I, II or III, if available)	Baseline
Tumor histology at initial diagnosis	SCC or adenocarcinoma	
Margins	Negative (clear), positive (involved), close margins	
	• 0: Fully active, able to carry on all pre-disease performance without restriction	
ECOG performance status	• 1: Restricted in physically strenuous activity but ambulatory and able to carry out work on a light or sedentary nature	
	
 
2: Ambulatory and capable of all self-care but unable to carry out work activities. Up and about more than 50% of waking hours
 
3: Capable of only limited self-care, confined to bed
 
	Baseline and all
	
 
or chair more than 50% of waking hours
 
4: Completely disabled. Cannot carry on any self-care. Totally confined to bed or chair
 
5: Dead
 
	visits 
Pathological lymph-node status	ypN0, ypN1, ypN2, ypN3, unknown	
Pathological tumor status	ypT0, ypT1, ypT2, ypT3, ypT4, unknown	
Biomarkers (if available)		
Tumor cell PD-L1 expression	Tumor cell PD-L1 expression levels and cells assessed. This will be used to group PD-L1 expression into $\geq 1\%$ , <1%, or Indeterminate/non-evaluable and to derive the combined positive score (CPS) score which is defined as PD-L1 positive tumor cells + PD-L1 positive mononuclear inflammatory cells)/Total tumor cells) × 100.	Baseline and all visits 
HER2 status	Positive, negative, not reported	
Tumor Mutational Burden (TMB)	Number of non-inherited mutations per million bases (Mb)	
Epstein-Barr virus positivity	Yes/No	Baseline
Microsatellite Instability (MSI)	Stable/Low/High	
Circulating tumor (ct) DNA	Absent/Detectable	

Variables	Definition	Timing
Metastasis	Yes/No	A 11:-:4-1
Sites of metastases	Lung, brain, liver, peritoneum, bone, lymph nodes, other	All VISITS

 Data will be collected at visits Day 0, and Months 3, 6, 9, 12, 18, 24, 30, 36, and 42.

Abbreviations: BMI body mass index; CPS= Combined Positive Score; ct=circulating tumor; DNA= Deoxyribonucleic Acid; EC = esophageal cancer; ECOG = Eastern Cooperative Oncology Group; GEJC = gastroesophageal junction cancer; HER=Herceptin; Mb=Million base; MSI=Microsatellite Instability; NCI = National Cancer Institute; OS = overall survival; PD-L1 = programmed cell death ligand-1; RCT = randomized controlled trial; TMB=Tumor Mutational Burden; US = United States

## 3.5.1.4 Incidence, Severity, and Management of AEs

This section describes the outcomes that will be used to evaluate the frequency, severity, and management of treatment-related AEs, select AEs, and other immune-related AEs. Data necessary to derive these outcomes will be collected if available. AE collection and reporting will follow the guidelines outlined in Section 7.1.

#### **Adverse Events**

An AE is any untoward medical occurrence in a patient or clinical investigation subject administered a pharmaceutical product, and which does not necessarily have to have a causal relationship with this treatment. An AE can therefore be any unfavorable and unintended sign (including an abnormal laboratory finding, for example), symptom, or disease temporally associated with the use of a medicinal product, whether or not considered related to the medicinal product.

#### **Treatment-related Adverse Events**

Treatment-related AEs are those events with a relationship to the study drug recorded as "Related" on the eCRF.

#### **Immune-related Select Adverse Events**

Among the immune-related AEs, a category of "select AEs" will be created to group the most common and impactful AEs, providing a better estimate of the frequency of similar types of organ-related AEs. These select AEs are further defined as follows:

- May differ from or be more severe than AEs caused by non-immunotherapies
- May require unique (non-standard) intervention such as immuno-suppressants (or hormone replacement therapy)
- Early recognition and management may mitigate severe toxicity

"Select AEs" category:

- Pneumonitis
- Diarrhea/Colitis
- Hepatitis
- Nephritis and renal dysfunction
- Endocrinopathies

- Pruritus
- Rash
- Severe infusion reactions

### **Other Immune-Related AEs**

In this study, immune-related AEs are defined as nivolumab treatment-related AEs that are consistent with the immune-based mechanisms of action of nivolumab, per investigator-assessed causality, and can occur during or after nivolumab treatment. Select AEs are special group of AEs, which follow the criteria listed above. Immune-related AEs that are not categorized as select AEs are considered as other immune-related AEs. Other immune-related AEs may include:

- Myocarditis
- Arthralgias
- Uveitis
- Pancreatitis
- Demyelination
- Guillain-Barre Syndrome
- Myasthenic syndrome
- Encephalitis

## 3.5.1.5 Patient-reported Outcome

In this study, patient satisfaction with nivolumab treatment will be assessed using the CTSQ at baseline and at the visits indicated in **Table 5**. In addition, three items form the FACT-G questionnaire will be assessed at baseline and at visits indicated in **Table 5**. Patient-reported outcomes will only be collected for 12 months, which is the treatment duration for nivolumab.

PRO	Definition	Timing
CTSQ	The revised CTSQ is 16-item instrument measuring three domains: Expectations of Therapy (5 items), Feelings about Side Effects (4 items), and Satisfaction with Therapy (7 items).	Day 0, and Months 3, 6, 9, and 12
FACT-G7	GP1 "I have lack of energy"	Day 0, and
	GP2 "I have pain"	Months 3, 6, 9, and 12
	GP3 "I have nausea"	
	GP4 "I worry that my condition will get worse"	
	GP5 "I am sleeping well"	
	GP6 "I am able to enjoy my life"	
	GP7 "I am content with the quality of my life right now"	

Table 5. Cancer Therapy Satisfaction Questionnaire

Abbreviations: CTSQ=Cancer Therapy Satisfaction Questionnaire; FACT-G7=Functional Assessment of Cancer Therapy – General 7

## 3.5.2 Other Covariates/Control Variables

**Table 6** list the variables that will be used to assess the representativeness of the study population.

Variables	Definition
Country	Country site (i.e., US, Germany)
Type of institution	Office-based/community hospital-based/university hospital-based
Specialization of the treating physician	Oncologist and/or treating physician
Hospital activity	Number of patients with EC/GEJC, as evaluated during feasibility assessment
Hospital location	Geographical region within each country

Table 6. Variables Used to Assess Sample Representativeness

Abbreviations: EC=Esophageal Cancer; GEJC=Gastroesophageal Junction Cancer; US=United States

## 4 STATISTICAL ANALYSIS

## 4.1 Statistical Analysis Methods

## 4.1.1 General Aspects

This study is purely descriptive, and no formal hypotheses will be tested. An overview of planned statistical analyses is provided in Sections 4.1.1 to 4.1.4. A standalone statistical analysis plan (SAP) will describe in detail all planned statistical analyses to be performed for this study.

The SAP will include tables, listings, figure shells to be populated during the interim and final data analyses, and details of changes in the planned analysis post-protocol finalization if applicable. It will also provide a description of the methods to deal with missing data, censoring, and procedures to control for potential sources of bias and their influence on the results.

All analyses will be conducted in accordance with the study objectives, SAP, and applicable guidelines. Statistical methods will be driven, in part, by the final sample size and the number of events. Results will be rounded to one decimal place; therefore, percentages may not always add up to 100. Standard deviation and 95% CIs will be calculated when relevant. The statistical analyses will be performed using SAS enterprise 7.1 or above, or SAS 9.4 or above. All patients who meet eligibility criteria will be included in the analysis data set.

## 4.1.1.1 Descriptive statistics

All collected data and outcomes will be analyzed using descriptive statistics and summarized in tables, listings, and figures as appropriate. Continuous variables will be described with summary statistics such as number of subjects, mean, standard deviation, median, first quartile, third quartile, and minimum and maximum values. For each categorical variable, the frequency and percentage in each category will be reported. Percentages will be calculated using the specified denominator in the table. The frequency and percentage of patients with missing data for each data point will be presented. For continuous and categorical variables, CIs of 95% will be calculated when relevant.

### 4.1.1.2 Time-to-Event Analyses

Time-to-event analysis will be used for outcomes that assess the length of time until the occurrence of a predefined outcome. The following time-to-event outcomes defined in Section 3.5.1 will be analyzed for all nivolumab patients, for patients that receive subsequent(s) treatments following nivolumab, and by subgroup of interests if sample size allows:

- DFS
- OS
- PFS2
- DMFS
- PRS

The time-to-event for each outcome during the study period will be reported in months, and summarized descriptively (minimum, median, quartiles, and maximum). Kaplan-Meier (KM) curves will be used to illustrate the survival probability estimates and the number of patients at risk over time for the overall population and by subgroup of interests when relevant. Median survival time estimates and survival probabilities (with two-sided 95% CIs) at each study period timepoint will be provided.

# 4.1.1.3 Missing Data

All efforts will be made to prevent missing data to the extent possible through various strategies set forth in the design and the conduct of the study. Should missing data occur, they will be analyzed as they are recorded in the study eCRFs and the level of missing data for all variables will be reported and the patterns of missing described. The impact of missing data on interpretation of findings will be acknowledged and discussed in the final study report. Further details on handling of missing data will be described in the SAP.

## 4.1.1.4 Subgroup Analyses

To meet the secondary and exploratory objectives, study outcomes will be summarized by subgroups of interest, depending on relevance, data availability and sample size including but not limited to:

- Patient and clinical characteristics:
  - o Country (US, Germany)
  - Sex (Male vs. female)
  - Age group ( $\leq 65$  vs. > 65)
  - o Race
  - Resection status (R0 vs R1)
  - Disease stage
  - o ECOG
  - Tumor location

- o Histology
- Pathologic lymph node status (ypN0 vs.  $\geq$  ypN1)
- Pathologic tumor status (ypT0 vs.  $\geq$  ypT1)
- Tumor cell PD-L1 expression
- Type of recurrence (local/regional vs. distant)

Furthermore, subgroup analyses (if sample size allows) will be performed according to Checkmate 577-like patient population vs. non-Checkmate 577 like patient population, using the key inclusion/exclusion criteria from the Checkmate-577 trial to determine the subgroups. This subgroup analysis will be performed to establish nivolumab safety and effectiveness in these two patient populations. If outcomes are similar between the two patient populations, this would support the use of nivolumab in almost all patients with EC and or GEJC.

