DFS	Time-to-event	Time between initiation of nivolumab treatment and the first date of recurrence (local, regional, or distant from the primary resected site) or death from any causes, whichever occurs first, as assessed by the investigator prior to subsequent anti-cancer therapy.
DFS rates	Continuous	DFS rates are defined as the probability that a patient is alive and presents no signs of recurrence at specific time points, following adjuvant nivolumab initiation.
08	Time-to-event	Time between initiation of nivolumab treatment until date of death due to any cause. Patients who are alive at last visit will be censored on date last known to be alive.
OS rates	Continuous	OS rates are defined as the probability that a patient is alive at specific time points, following adjuvant nivolumab initiation.
DMFS	Time-to-event	Time between initiation of nivolumab treatment and date of appearance of distant metastasis or death from any causes, whichever occurs first, as assessed by the investigator prior to subsequent anti-cancer therapy.
DMFS rates	Continuous	DFS rates are defined as the probability that a patient is alive and presents no signs of metastasis at specific time points, following adjuvant nivolumab initiation.
Time to recurrence	Continuous	Time between initiation of nivolumab treatment and the first date of recurrence.
Recurrence rates	Categorical	Recurrence rates are defined as disease recurrence (i.e., local/regional, metastatic) at specific time points, following adjuvant nivolumab initiation.
PRS	Time-to-event	PRS is defined as the interval from the date of any recurrence to the date of death from any cause. Patients who are alive at last visit will be censored on date last known to be alive.
Effectiveness outcomes in pati discontinuation:	ients that receive s	ubsequent treatment(s) following adjuvant nivolumab
OS of subsequent treatment	Time-to-event	Time between initiation of subsequent treatment until date of death due to any cause. Patients who are alive at last visit will be censored on date last known to be alive.
OS rates of subsequent treatment	Continuous	OS rates are defined as the probability that a patient is alive at specific time points, following subsequent treatment initiation.

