## 4.1.3 Analysis Plan for Secondary Objectives

## 4.1.3.1 Secondary Effectiveness Outcomes

The analysis of OS and DMFS for all nivolumab patients and OS and PFS2 for patients that receive subsequent treatment following nivolumab treatment discontinuation will be performed following a similar procedure as for DFS (see Section 4.1.2) and will be estimated and plotted using the KM estimator overall and by subgroup of interests.

- Median DFS in subgroup of interest (overall DFS is assessed a primary outcome) and DFS rates will be estimated and reported along with the corresponding two-sided 95% Cis
- Median OS with the corresponding two-sided 95% CIs will be reported. OS rates will be estimated and reported along with the corresponding two-sided 95% CIs.

- Median DMFS and the corresponding two-sided 95% CIs will be estimated. DMFS rates will be estimated and the corresponding two-sided 95% CIs will be reported.
- Median PFS2 and the corresponding two-sided 95% CIs will be estimated. PFS2 rates will be estimated and the corresponding two-sided 95% CIs will be reported.
- Median ORR the corresponding two-sided 95% CIs
- Where adequate follow-up data is available median DFS, OS, PFS2, DMFS and ORR with their corresponding two-sided 95% CIs will be estimated in subgroup of interests (see section 4.1.1.4) as described for the overall population.

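### Type of recurrence is listed as a subgroup for DFS, OS and DMFS counted from nivolumab start, although it is known only after recurrence, which is itself a DFS event

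*Protocol*

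**What the plan says.** Protocol section 4.1.1.4 sets the general rule that "study outcomes will be summarized by subgroups of interest, depending on relevance, data availability and sample size including but not limited to" a list headed as patient and clinical characteristics. The list runs from country and sex through stage, histology and PD-L1 and ends with "Type of recurrence (local/regional vs. distant").

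Section 4.1.3.1 applies that list by cross-reference. Where follow-up is adequate, "median DFS, OS, PFS2, DMFS and ORR with their corresponding two-sided 95% CIs will be estimated in subgroup of interests (see section 4.1.1.4") in the same way as for the overall population. An earlier bullet in that section adds: "Median DFS in subgroup of interest (overall DFS is assessed a primary outcome) and DFS rates will be estimated". Section 4.1.1.2 plans Kaplan-Meier analyses of DFS, OS, PFS2, DMFS and PRS by subgroup.

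The time origins are in Table 2 (section 3.5.1.1):

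- **DFS:** "Time between initiation of nivolumab treatment and the first date of recurrence (local, regional, or distant from the primary resected site) or death", with the qualifier "as assessed by the investigator prior to subsequent anti-cancer therapy".
- **OS:** "Time between initiation of nivolumab treatment until date of death due to any cause".
- **DMFS:** also from nivolumab start, to distant metastasis or death.
- **PRS:** from the date of recurrence to death.

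Table 1 defines recurrence as relapse that the investigator detects in follow-up after nivolumab has started.

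**The concern.** A subgroup for a survival curve should be identifiable at the curve's time zero. Type of recurrence is not: it becomes known only when the patient relapses. For DFS the difficulty is sharper still, because the relapse is the event being timed. Patients are sorted by having had the event, and the time to that event is then estimated.

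The resulting tables would carry the labels DFS, OS and DMFS but would describe no group of patients who could be recognised when treatment starts. The synopsis and section 5.2 intend the results for guideline committees and regulatory authorities. A reader could set a median DFS of about 11 months in recurrers beside the overall median and take it as a property of a patient type.

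**Working it through.** The protocol states no figure for these subgroup analyses, so there is none to reproduce. The structural argument comes first and needs no numbers.

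**What follows from the definitions**

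| Outcome from nivolumab start | Local/regional group | Distant group |
|---|---|---|
| DFS | every counted recurrence is a DFS event, so the curve ends at zero | same |
| DMFS | later metastasis or death; membership still fixed in the future | the grouping event is the endpoint event, so the curve ends at zero |
| OS | every member is certain to be alive until recurrence | same |

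Patients without an observed recurrence, including those who die without one, are in neither group.

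**Size for DFS**

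Inputs from the protocol: 40% DFS at two years and N = 314 (section 4.2); follow-up between 24 months (last patient in) and 42 months (first patient in) (synopsis and section 3.1). Assumed: exponential DFS, administrative censoring uniform on 24–42 months, recurrence share constant over time, no drop-out at first.

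1. Hazard: λ = −ln(0.40)/24 = 0.03818 per month.
2. Whole cohort: median = ln 2/λ = 18.2 months. DFS at 12, 24 and 36 months is 63%, 40% and 25%, and at 42 months exp(−42λ) = 20%.
3. Probability that a first event is seen within follow-up: 1 − [exp(−24λ) − exp(−42λ)]/(18λ) = 1 − (0.4000 − 0.2012)/0.6872 = 0.7107.
4. Observed recurrers all have the event, so their Kaplan-Meier curve is one minus the distribution of their event times. At 24 months: (0.7107 − 0.6000)/0.7107 = 15.6%. At 12 months: (0.7107 − 0.3675)/0.7107 = 48.3%. At 36 months it is about 1%, and at 42 months zero.
5. Median among recurrers: solve 1 − exp(−λt) = 0.7107/2 = 0.3553, giving t = −ln(0.6447)/0.03818 = 11.5 months.
6. With 10% exponential drop-out by month 24 (the rate is the protocol's, its timing assumed), the same calculation gives 11.0 months and 14.5%.

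The recurrence share cancels from steps 4 to 6, so these figures do not depend on it. With the split between local/regional and distant independent of time, the two DFS curves coincide.

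**Patients in neither group**

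If 10–30% of first events are deaths, and without drop-out: 314 × (1 − 0.7107 × 0.90) = 113, up to 314 × (1 − 0.7107 × 0.70) = 158 of 314.

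**OS and DMFS**

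These need further assumptions that the protocol does not supply: median survival after recurrence of 12 months (distant) or 18 months (local/regional), a median of 18 months from local/regional recurrence to metastasis, and 50–70% of recurrences distant. A simulation of 200,000 patients without drop-out gave:

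- 12-month OS of 89% in the local/regional group against 82–88% overall. Patients who relapsed appear to do at least as well as the whole cohort, because they could not die before relapse.
- 24-month OS of about 67% (local/regional) and 57% (distant).
- DMFS ending at 0.000 in the distant group and at about 0.15 in the local/regional group.
- DFS ending at 0.000 in both groups in every scenario, with medians of 11.4–11.6 months, in agreement with step 5.

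**The case against.** The strongest defence is that the protocol never pairs type of recurrence with DFS, OS or DMFS by name. Section 4.1.1.4 is one menu for all outcomes, qualified by relevance, data availability and sample size. Section 4.1.1.2 repeats such conditions, and section 4.1.3.1 requires adequate follow-up. The same menu serves PRS and outcomes from subsequent treatment, where the grouping can be legitimate, and the entry may have been meant for those. The detailed analyses are left to a separate SAP.

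Part of this stands. A reader might infer that the sponsor is bound to produce these curves; the conditional wording does not support that. But none of the conditions confines this subgroup to outcomes starting at recurrence, and adequate follow-up does not screen it out, since recurrers have complete DFS data. Section 4.1.3.1 points to the list in 4.1.1.4, not to the SAP, so this is a stated rule and not a detail left for later.

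Three further readings go too far:

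- **That any difference between the two types reflects only the timing of recurrence and not prognosis.** This fits DFS. It fails for OS, which includes survival after recurrence; the 67% against 57% above arises largely from the different post-recurrence survival assumed.
- **That DFS must reach exactly zero.** Table 2 counts events assessed before subsequent anti-cancer therapy. A recurrence first found afterwards may not count, so the curve could stop slightly above zero.
- **That the entry should be deleted.** The list is not labelled as baseline, and the grouping is sound for PRS.

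**Conclusion.** Wrong as written, of moderate severity. Followed literally, sections 4.1.1.4 and 4.1.3.1 give DFS curves that fall essentially to zero in both groups, a distant-group DMFS defined by its own event, and OS with immortal time up to recurrence. This rests on the endpoint definitions alone.

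The size is an illustration under exponential DFS and uniform administrative censoring: median DFS of about 11 months in observed recurrers against 18 overall, and 24-month DFS of about 14–16% against 40%. The OS and DMFS figures depend more heavily on assumed values and show direction only.

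A reader might take this as a threat to the main result. It is not: the primary outcome is overall median DFS, which does not use this subgroup. The study is descriptive, the affected analyses are secondary and conditional, and no sample size or eligibility rule is touched.

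**What to change.** State in sections 4.1.1.4 and 4.1.3.1 that type of recurrence is used as a subgroup only for outcomes whose time origin is at or after recurrence: PRS, and OS, PFS2 and ORR from subsequent treatment that began after the recurrence. The last condition matters because Table 2 does not limit the subsequent-treatment population to patients who have already relapsed.

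To describe local/regional and distant recurrence from nivolumab start, report the cumulative incidence of each type in the whole cohort, with the other type of first recurrence and death without recurrence as competing events.

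The cost is a clause in two protocol sections and matching SAP wording before database lock. Table 3 already collects the date and type of recurrence and the date of death, so no new data are needed and the sample size does not change.

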# 3.3 Study Population

### 3.3.1 Inclusion Criteria

To be enrolled in the study patients must meet the following criteria:

- 1. Patients aged 18 years or older at the time of informed consent
- 2. Patients provide voluntary informed consent to participate in the study before inclusion in the study
- 3. Confirmed diagnosis of resected early-stage (Stage II/III) EC or GEJC (histologically or cytologically confirmed stage)
- 4. Physician decision to treat the patient with adjuvant nivolumab (according to the local label as per country-specific regulations) must be made prior to and independently of participation in the study

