### Hawthorne effect

Participation in an observational study may influence physicians' behaviors and adjust their practice regarding nivolumab treatment and EC/GEJC patient management. The potential for this bias has been acknowledged and, in this study, only incident (new) users of nivolumab will be included and no comparison will be made with prevalent nivolumab users.

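### Similar outcomes in CheckMate 577-like and non-like patients cannot show that nivolumab benefits the non-like group, nor support its use in almost all patients

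*Protocol*

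**What the plan says.** Section 4.1.1.4 provides that "subgroup analyses (if sample size allows) will be performed according to Checkmate 577-like patient population vs. non-Checkmate 577 like patient population", with the groups formed from the trial's key eligibility criteria. It gives the purpose as follows: "This subgroup analysis will be performed to establish nivolumab safety and effectiveness in these two patient populations". The closing sentence says that if the two groups have similar outcomes, "this would support the use of nivolumab in almost all patients with EC and or GEJC".

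Four other parts of the protocol bear on this:

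- Section 4.1.1: "This study is purely descriptive, and no formal hypotheses will be tested".
- Section 5.1, Hawthorne effect: "only incident (new) users of nivolumab will be included". Together with section 3.1, this makes the study a single treated cohort.
- Section 3.3.1: criterion 3 requires "Confirmed diagnosis of resected early-stage (Stage II/III) EC or GEJC", and criterion 4 requires "Physician decision to treat the patient with adjuvant nivolumab (according to the local label as per country-specific regulations").
- Section 1.1 describes the US and European approvals as covering resected disease with residual pathologic disease after neoadjuvant chemoradiotherapy.

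**The concern.** The benefit of a treatment is the outcome with it minus the outcome without it. This study observes only the first term. Finding that two treated groups do about equally well says how treated patients fared. It does not say what treatment added for the group that has no randomised comparison to draw on.

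The closing sentence also moves from the enrolled patients to nearly everyone with these cancers, although the eligibility criteria exclude most of that wider population by design. The synopsis and section 5.2 say the results will inform guideline committees and regulatory authorities. A sentence written in advance that turns similarity into support for wider use could therefore be cited as if the design had earned it. The limitations in section 5.1 do not qualify it.

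**Working it through.** **1. What similarity identifies.** Write S1 for DFS at a given time with nivolumab and S0 for DFS at that time without it.

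- Benefit in the like group = S1(like) − S0(like).
- Benefit in the non-like group = S1(non) − S0(non).

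The study estimates S1(like) and S1(non). For the like group, section 1.1 supplies an outside randomised contrast: median DFS 22.4 against 11.0 months, hazard ratio 0.69 (96.4% CI 0.56 to 0.86). For the non-like group, nothing in the protocol supplies S0(non). Suppose S1(non) = S1(like) = 40% at 24 months. The benefit in the non-like group is then 40% − S0(non). That is zero if untreated patients of that kind would also reach 40%, and positive if they would do worse. The same observed similarity fits either case.

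**2. Population sampled against population named.**

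| Source | Population |
|---|---|
| Section 3.3.1, criterion 3 | Resected, stage II/III |
| Section 3.3.1, criterion 4, with section 1.1 | Treated according to the local label, described as residual disease after neoadjuvant chemoradiotherapy |
| Section 5.1, Selection bias | Early-stage patients initiating adjuvant nivolumab in the US or Germany |
| Section 4.1.1.4, last sentence | Almost all patients with EC and/or GEJC |

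The last row is wider than each of the others, including the protocol's own target population.

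**3. How much similarity could show (illustration only).** The plan gives no figure for this comparison and does not state the non-like share. The inputs are:

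- Section 4.2: N = 314 with 10% drop-out, so 314 × 0.90 = 282.6, about 283 evaluable.
- Section 4.2: DFS 40% at two years, taken as true in both groups, so the variance term is 0.40 × 0.60 = 0.24.
- Assumed: non-like shares of 50%, 20% and 10%.

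Half-width of the 95% CI for the difference = 1.96 × sqrt(0.24/n1 + 0.24/n2).

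| Assumed non-like share | n non-like | n like | Half-width |
|---|---|---|---|
| 50% | 141.5 | 141.5 | 1.96 × sqrt(0.00170 + 0.00170) = 11.4 points |
| 20% | 56.6 | 226.4 | 1.96 × sqrt(0.00424 + 0.00106) = 14.3 points |
| 10% | 28.3 | 254.7 | 1.96 × sqrt(0.00848 + 0.00094) = 19.0 points |

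This treats DFS at 24 months as a simple proportion and ignores further censoring. At a 20% share, an observed difference of zero would still be compatible with the non-like group being about 14 points worse or better.

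The figure of 285 in Table 7, from which 314 comes (285 × 1.10 = 313.5), is not what the usual formula gives: 1.96² × 0.24 / 0.07² = 188.2, so 189. That is a separate matter. Here N only sets the scale of the illustration, and steps 1 and 2 use no figure for N.

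**The case against.** The strongest reply is that this is one conditional sentence about a secondary subgroup summary. It sets no threshold, test or action, and the analysis runs only if sample size allows. That is correct. A reader might call it the plan's decision rule, but the text does not support that. No eligibility criterion, endpoint or estimator depends on it.

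Three other strong readings also fail:

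- **That the study says nothing about benefit in either group.** The like group is defined by the criteria of a placebo-controlled trial summarised in section 1.1, so it can draw on that evidence. The gap concerns the non-like group.
- **That better prognosis would hide a lack of effect**, citing the five-year survival of 50% with pathological complete response against 37% without in section 1.1. Those figures are five-year survival, not 24-month DFS. If entry is on-label as section 1.1 describes it, complete responders are not the patients enrolled. The direction is not settled either: the trial required R0 resection, while section 4.1.1.4 lists an R1 subgroup.
- **That the absence of a margin for similarity is a defect in itself.** Section 4.1.1 leaves analysis detail to a separate SAP, which may define one. A margin would not supply a comparator or widen the population.

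Two further replies carry some weight. The wider phrase could be read within the target population of section 5.1, although the sentence does not say so, and step 1 of the working applies on that reading too. Section 4.1.1 rules out formal hypotheses and section 4.1.1.4 specifies none, so the conflict lies in the words *establish* and *support*, not in the analysis.

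**Conclusion.** The point holds as a fault of interpretation written into section 4.1.1.4. Similar outcomes among treated patients cannot establish effectiveness in the non-like group. The enrolled population does not extend to almost all patients with these cancers. Neither statement fits a purely descriptive study. This rests on the design as stated and needs no numerical assumption.

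The half-widths of about 14 and 19 points do depend on assumed shares of 20% and 10%, about 283 evaluable patients and 40% DFS in both groups. They show only that apparent similarity would be weak evidence.

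A reader might infer that the primary result is compromised. It is not: the overall DFS estimate and every other planned estimate stand unchanged. Severity is therefore should-fix.

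**What to change.** In section 4.1.1.4:

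1. Delete the closing sentence, the one that draws a conclusion from similar outcomes.
2. In the preceding sentence, change the purpose from establishing safety and effectiveness to *describing safety and outcomes* in the two groups.
3. Add the 95% CI of the between-group difference. The per-group intervals are already planned: section 4.1.1.2 provides "Median survival time estimates and survival probabilities (with two-sided 95% CIs"), and section 4.1.3.1 extends this to subgroups.
4. State that no inference of treatment benefit will be drawn from similarity, and that findings apply to the enrolled patients: resected stage II/III disease treated according to the local label.

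The cost is a protocol wording change and one added interval. It needs no new patients or data. The sponsor gives up a claim that the design cannot support.
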